### 8.4 Physical Examinations

Physical examination data will be listed by subjects.

### 8.5 Clinical Laboratory

Clinical laboratory tests include serum chemistry, hematology, urinalyses and other lab analyses. Potentially clinically relevant laboratory test abnormalities will be listed by subject and by test. Criteria for potentially clinically relevant laboratory test abnormalities are provided in [Appendix 2](#). Subjects with aspartate aminotransferase (AST) or alanine aminotransferase (ALT)  $\geq$  3 x upper limit of normal value and total bilirubin  $\geq$  2 x upper limit of normal value will be listed. The incidences of potentially clinically relevant laboratory tests abnormalities based on observations during scheduled and unscheduled post-baseline visits will be tabulated by treatment formulation and disease type. Summary statistics for clinical laboratory measurements and changes from baseline will be presented by trial visit, treatment formulation and disease type.

If laboratory tests assessments are repeated for the same mapped trial visit, the last repeated values will be used for summary tables. This is accomplished by sorting patient data by visit date and visit time (if applicable) within the same trial visit. If the lab data are recorded as ranges (i.e., including < or > limit of quantification), these data are not

Protocol 031-201-00181

included in the calculations for changes from baseline but included in the calculations for incidences.

The incidence of prolactin level above the upper limit of normal range (potentially clinically relevant change) will be calculated by treatment formulation and disease type. Summary statistics (mean, standard deviation, median, minimum, and maximum) and changes from baseline in prolactin concentration will be presented by trial visit, treatment formulation and disease type. Similar analyses will be performed for male and female, respectively. Additionally, incidences of treatment-emergent relevant changes in lipid parameters and glucose (as defined in [Table 8.5-1](#)) will be summarized by treatment formulation and disease type, though those blood samples are not required to be collected at the fasted state.

Table 8.5-1 Criteria for Treatment-emergent Relevant Changes in Lipids Parameters and Glucose		
Parameters	Baseline	Any Post-baseline
Total Cholesterol (mg/dL)		
	Normal <200	High $\geq$ 240
	Borderline 200~<240	High $\geq$ 240
	Normal/Borderline <240	High $\geq$ 240
	Normal <200	Borderline/High $\geq$ 200
	Any Value	Increased $\geq$ 40
LDL Cholesterol (mg/dL)		
	Normal <100	High $\geq$ 160
	Borderline 100~<160	High $\geq$ 160
	Normal/Borderline <160	High $\geq$ 160
	Normal <100	Borderline/High $\geq$ 100
	Any Value	Increased $\geq$ 30
HDL Cholesterol (mg/dL)		
	Normal $\geq$ 40	Low <40
	Any Value	Decreased $\geq$ 20
Triglycerides (mg/dL)		
	Normal <150	High $\geq$ 200
	Normal <150	Very High $\geq$ 500
	Borderline 150~<200	High $\geq$ 200
	Borderline 150~<200	Very High $\geq$ 500
	Normal/Borderline <200	High $\geq$ 200
	Normal/Borderline <200	Very High $\geq$ 500
	Normal <150	Borderline/High/Very High $\geq$ 150
	Normal/Borderline /High $\geq$ 200	Very High $\geq$ 500
	Any Value	Increased $\geq$ 50
Glucose (mg/dL)		
	Normal <100	High $\geq$ 126
	Impaired Fasting Glucose 100~<126	High $\geq$ 126

Protocol 031-201-00181

Table 8.5-1 Criteria for Treatment-emergent Relevant Changes in Lipids Parameters and Glucose		
Parameters	Baseline	Any Post-baseline
	Normal/ Impaired Fasting Glucose <126	High $\geq 126$
	Any Value	Increased $\geq 10$

Note: The National Cholesterol Education Program (NCEP) Adult Treatment Program Classifications of lipids (refer to fasting lipid measurements) are used for lipid parameters and the American Diabetes Association Criteria are used for glucose.

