**Table 3.4.3-1      Exclusion Criteria**

|     |   |
|-----|---|
| 16. | History of any significant drug allergy or known or suspected hypersensitivity, in particular to aripiprazole or other quinolinones.  |
| 17. | History of or current hepatitis or acquired immunodeficiency syndrome or carriers of HBsAg or anti-HCV, and/or HIV antibodies.  |
| 18. | Subjects deemed intolerant of receiving injections.   |
| 19. | Subjects who have had electroconvulsive therapy within 2 months of administration of IMP.   |
| 20. | The following laboratory test, vital sign, and ECG results are exclusionary:
1) Platelets $\leq$ 75,000/mm 
2) Hemoglobin $\leq$ 9 g/dL
3) Neutrophils, absolute $\leq$ 1000/mm 
4) AST $>$ 3x upper limit of normal
5) ALT $>$ 3x upper limit of normal
6) Creatinine $\geq$ 2 mg/dL
7) Diastolic blood pressure $>$ 105 mmHg
8) QTcF $\geq$ 450 msec in males or $\geq$ 470 msec in females, on 2 of 3 time points of triplicate ECGs performed |

anti-HCV = hepatitis C antibodies; ALT = alanine aminotransferase; AST = aspartate aminotransferase;

C-SSRS = Columbia-Suicide Severity Rating Scale; FOCBP = females of childbearing potential;

HBsAg = hepatitis B surface antigen; HIV = human immunodeficiency virus; QTcF = corrected QT interval using Fridericia's formula; ULN = upper limit of normal.

Subjects excluded for a positive drug screen for drugs of abuse are not eligible to be rescreened for participation in the trial. For those who test positive for alcohol and/or marijuana, and for those who test positive for a drug of abuse for which they have a prescription, the investigator must provide sufficient written rationale and discuss with the medical monitor before attaining clearance to proceed with enrollment. This rationale must include the following: 1) rationale/indication for use, 2) review of patterns of use and frequency of use, and 3) justification to support compliance with the protocol for the intended duration of treatment (eg, based on investigator conversation with the subject).

Subjects excluded for other reasons may be rescreened at any time if the exclusion characteristic has changed. In the event that the subject is rescreened, a new ICF must be signed, a new screening number assigned, and all screening procedures repeated.

Rescreening of subjects is described in [Section 3.9](#).

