## 8 Safety Analyses

Safety assessments including adverse events (AEs), vital signs, ECGs, clinical laboratory monitoring (serum chemistry, hematology, urinalysis), physical examinations, EPS, VAS scores for pain perception, investigator's assessment of most recent injection site, and suicidality via the C-SSRS will be summarized for the safety sample by treatment formulation and disease type in addition to all treated subjects.

In summarizing the incidence of clinically relevant abnormalities in clinical laboratory results, vital sign measurements and ECG measurements, a subject must have had an evaluation that meets the specified criteria. Incidence rate will be calculated as the number of subjects having at least 1 abnormality in the treatment phase divided by the number of subjects in the safety sample.

Safety data collected during in-clinic visits and virtual visits are summarized together.

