## Appendix 1                      Criteria for Identifying Vital Sign Values of Potential Clinical Relevance

Variable	Criterion Value a	Change Relative to Baseline a
Heart Rate b	> 120 bpm	≥ 15 bpm increase
	< 50 bpm	≥ 15 bpm decrease
Systolic Blood Pressure b	> 180 mmHg	≥ 20 mmHg increase
	< 90 mmHg	≥ 20 mmHg decrease
Diastolic Blood Pressure b	> 105 mmHg	≥ 15 mmHg increase
	< 50 mmHg	≥ 15 mmHg decrease
Orthostatic Hypotension	≥ 20 mmHg decrease in systolic blood pressure and a ≥ 25 bpm increase in heart rate from supine to sitting/standing	Not Applicable
Weight	-	≥ 7% increase ≥ 7% decrease
Temperature	≥ 37.8°C	≥ 1.1°C increase

a In order to be identified as potentially clinically relevant, an on-treatment value must meet the “Criterion Value” and also represent a change from the subject’s baseline value of at least the magnitude shown in the “Change Relative to Baseline” column.

b As defined in “Supplementary Suggestions for Preparing an Integrated Summary of Safety Information in an Original NDA Submission and for Organizing Information in Periodic Safety Updates,” FDA Division of Neuropharmacological Drug Products draft (2/27/87).

Protocol 031-201-00181

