## Appendix 2      Criteria for Identifying Laboratory Values of Potential Clinical Relevance

Laboratory Tests	Criteria
Chemistry	
AST (SGOT)	≥ 3 x upper limit of normal (ULN)
ALT (SGPT)	≥ 3 x ULN
Alkaline phosphatase	≥ 3 x ULN
LDH	≥ 3 x ULN
BUN	≥ 30 mg/dL
Creatinine	≥ 2.0 mg/dL
Uric acid	
Men	≥ 10.5 mg/dL
Women	≥ 8.5 mg/dL
Bilirubin (total)	≥ 2.0 mg/dL
CPK	≥ 3 x ULN
Prolactin	> ULN
Hematology	
Hematocrit	
Men	≤ 37 % and decrease of ≥ 3 percentage points from baseline
Women	≤ 32 % and decrease of ≥ 3 percentage points from baseline
Hemoglobin	
Men	≤ 11.5 g/dL
Women	≤ 9.5 g/dL
White blood count	≤ 2,800 mm  or ≥ 16,000 mm 
Eosinophils	≥ 10%
Neutrophils	≤ 1,500/mm 
Platelet count	≤ 75,000/mm  or ≥ 700,000/mm 
Urinalysis a	
Protein	Increase of ≥ 2 units
Glucose	Increase of ≥ 2 units
Casts	Increase of ≥ 2 units
Additional Criteria	
Chloride	≤ 90 mEq/L or ≥ 118 mEq/L
Potassium	≤ 3.0 mEq/L or ≥ 5.5 mEq/L
Sodium	≤ 126 mEq/L or ≥ 156 mEq/L
Calcium	≤ 8.2 mg/dL or ≥ 12 mg/dL
Glucose	
Fasting	≥ 115 mg/dL
Non-fasting	≥ 200 mg/dL
Total cholesterol, fasting	≥ 240 mg/dL
LDL cholesterol, fasting	≥ 160 mg/dL
HDL cholesterol, fasting	≤ 30 mg/dL
Triglycerides, fasting	
Men	≥ 160 mg/dL
Women	≥ 120 mg/dL

a As defined in "Supplementary Suggestions for Preparing an Integrated Summary of Safety Information in an Original NDA Submission and for Organizing Information in Periodic Safety Updates," FDA Division of Neuropharmacological Drug Products draft (2/27/87).

Protocol 031-201-00181

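### Most SAP Appendix 2 laboratory criteria have no baseline condition, so an abnormality present at baseline and seen again after dosing is tabulated like a new one, most clearly for prolactin

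*SAP*

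**What the plan says.** SAP section 8 sets the incidence rule for laboratory, vital sign and ECG abnormalities: "the number of subjects having at least 1 abnormality in the treatment phase divided by the number of subjects in the safety sample". Section 8.5 says which laboratory values feed it: "The incidences of potentially clinically relevant laboratory tests abnormalities based on observations during scheduled and unscheduled post-baseline visits will be tabulated". Neither sentence sets aside subjects who already met the criterion before the first injection.

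The criteria are in SAP Appendix 2. Nearly all are absolute limits. The exceptions are hematocrit (for men, "≤ 37 % and decrease of ≥ 3 percentage points from baseline"; women have the same change condition with a lower limit) and urinalysis protein, glucose and casts, each defined as "Increase of ≥ 2 units". Prolactin is flagged whenever it exceeds the upper limit of normal (ULN), and the text of 8.5 describes that as a change: "The incidence of prolactin level above the upper limit of normal range (potentially clinically relevant change) will be calculated".

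Appendix 1 (vital signs) is built differently. Its footnote a requires the criterion value "and also represent a change from the subject’s baseline value" of a set size. Appendix 3 (ECG) carries the same footnote.

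**The concern.** Laboratory monitoring is part of the primary safety endpoint, and the by-formulation incidence table is where a reader will look for laboratory effects of the two injections. As defined, that table cannot separate a subject who became abnormal after dosing from one who arrived abnormal and stayed so, or even from one who improved but not below the limit.

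The SAP conditions on baseline in comparable places: Appendices 1 and 3, the new-onset QTc categories in 8.6, and the lipid and glucose rules in Table 8.5-1. Appendix 2 is the exception. At stake is whether the reported incidences can be read as treatment-emergent, and whether a real difference in new abnormalities would still be visible once pre-existing cases are mixed in.

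**Working it through.** There is no sample size, power or alpha figure to reproduce here. The check sets the criteria side by side and then illustrates the effect.

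**1. Can a subject qualify at entry?** Entry limits are from Protocol Table 3.4.3-1, Exclusion 20 (for example "2) Hemoglobin $\leq$ 9 g/dL"). Flags are from SAP Appendix 2.

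| Test | Allowed at entry | Flagged | Overlap |
|---|---|---|---|
| Hemoglobin, men | > 9 g/dL | ≤ 11.5 g/dL | > 9 to 11.5 |
| Hemoglobin, women | > 9 g/dL | ≤ 9.5 g/dL | > 9 to 9.5 |
| Neutrophils | > 1000/mm3 | ≤ 1500/mm3 | > 1000 to 1500 |
| AST, ALT | ≤ 3x ULN | ≥ 3x ULN | only exactly 3x ULN |
| Creatinine | < 2 mg/dL | ≥ 2.0 mg/dL | none |
| Platelets, low side | > 75,000/mm3 | ≤ 75,000/mm3 | none |
| Prolactin, CPK, bilirubin, uric acid, eosinophils and some others | no numeric limit | see Appendix 2 | possible, subject to judgement |

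The judgement in the last row is the investigator's, on whether a deviation is clinically significant (Inclusion 4, Exclusion 9).

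**2. When is such a subject counted?** Only if the criterion is met again at a post-baseline visit. Hematology and chemistry are scheduled after baseline at Day 29 and Day 225/early termination. Prolactin is scheduled after baseline only at Day 29 (Protocol Tables 3.7-1 and 3.7-2), so its incidence rests on essentially one value per subject.

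**3. What does this do to the table?** Let b be the share meeting the criterion at baseline, q the share of those meeting it again after baseline, and r the new-onset rate in the rest. Then

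reported incidence = b·q + (1 − b)·r.

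The documents give none of the three, so the values below are assumptions. With r = 5%:

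| b | q | b·q + (1 − b)·r | Reported | Share of counted cases already present at baseline |
|---|---|---|---|---|
| 5% | 0.5 | 0.025 + 0.0475 | 7.3% | 34% |
| 10% | 0.8 | 0.080 + 0.045 | 12.5% | 64% |
| 20% | 0.8 | 0.160 + 0.040 | 20.0% | 80% |
| 40% | 0.8 | 0.320 + 0.030 | 35.0% | 91% |

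Counting only subjects who did not meet the criterion at baseline returns 5% in every row.

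**4. Between arms.** Take true new-onset rates of 10% and 5% (ratio 2.0), with the same b and q in both arms.

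- b = 10%, q = 0.8: (0.08 + 0.09)/(0.08 + 0.045) = 0.170/0.125 = 1.36.
- b = 30%, q = 0.8: (0.24 + 0.07)/(0.24 + 0.035) = 0.310/0.275 = 1.13.

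The difference shrinks less, from 5.0 percentage points to 4.5 and 3.5.

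**5. In subjects.** With 129 per group, if 10 to 30% enter above the prolactin ULN and half remain above it, 129 × 0.10 × 0.5 ≈ 6 to 129 × 0.30 × 0.5 ≈ 19 subjects per arm are counted with no new abnormality. If 2 to 4% enter in the hemoglobin or neutrophil band, the same 50% persistence gives 129 × 0.02 × 0.5 ≈ 1 to 129 × 0.04 × 0.5 ≈ 3.

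**The case against.** The strongest reply is that an absolute threshold is a deliberate, cautious screen. It over-counts rather than hides, no laboratory hypothesis is tested, and baseline is used elsewhere. SAP 8.5 plans changes from baseline for all laboratory tests, prolactin changes repeated by sex, listings by subject and test, and Table 8.5-1. Protocol 5.1 has the investigator judge each abnormal result against that subject's baseline and record relevant ones as adverse events. SAP 8.10 tabulates treatment-emergent prolactin, glucose, lipid and white-cell events. At screening, Protocol 3.7.6.2 also bars a subject with a clinically significant result unless the medical monitor permits enrolment.

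Much of this stands. It is a reason to keep the absolute count, and it shows that the weakness lies in one table, not in the whole laboratory assessment. It does not close the gap. Mean changes and listings do not give the number newly abnormal by arm, Table 8.5-1 covers only lipids and glucose, and the entry safeguards turn on clinical significance rather than on the Appendix 2 limits.

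Three stronger readings are tempting, and the documents do not support them.

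- A reader might infer that every pre-dose abnormality is counted. It is not: the value must qualify again after baseline.
- A reader might infer that Appendix 2 overlaps the entry limits throughout. It does not for creatinine or low platelets, and AST and ALT touch at a single value.
- A reader might infer a spurious difference between formulations. Allocation is 1:1 and stratified by disease type, so pre-existing abnormalities balance in expectation. Persistence could differ somewhat, because sparse-schedule subjects on another oral antipsychotic continue it for 7 days in one arm and 14 in the other (Protocol 3.2.3). The documents give no size or direction for any effect on prolactin, so the point does not rest on it.

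**Conclusion.** The point holds as a limited one. For Appendix 2 tests other than hematocrit and the urinalysis items, the planned incidence combines abnormalities already present at baseline with new ones. This is possible by the numbers for hemoglobin and neutrophils, and possible subject to investigator judgement for tests with no entry limit. Prolactin is the clearest case: the threshold is the ULN itself, there is one scheduled post-baseline sample, and the result is labelled a change.

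The expected effect is a raised incidence in each arm and a between-arm ratio drawn toward 1. How large it is depends on baseline prevalence and persistence, which the documents do not state. The figures above show the form of the effect and are not estimates for this trial. The analysis is descriptive and the primary pharmacokinetic conclusions are untouched, so this is an inexpensive improvement to a safety table.

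**What to change.** In SAP 8.5 and Appendix 2, keep the absolute-value incidence and add a treatment-emergent incidence beside it. The numerator is subjects who meet the criterion after baseline and did not meet it at baseline, as baseline is defined in SAP 5.1. The denominator is subjects who did not meet it at baseline and have a post-baseline value. Hematocrit and the urinalysis items can stay as they are.

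For prolactin, add a baseline-by-Day 29 shift table (normal/high) by treatment formulation and disease type. In the text, describe the existing prolactin count as a level above ULN rather than as a change.

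The cost is SAP wording, one baseline flag per test and some extra table columns, all from data already collected. One small downside should be stated in the SAP: worsening in a subject already abnormal at baseline will not appear in the new column, only in the absolute count, the change summaries and the listings. That is why the absolute count should stay.

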### **3.7.1 General Inpatient Procedures**

Subjects enrolled to the robust sampling schedule who receive aripiprazole 2M LAI 960 mg must be housed in the clinical unit for 21 days after the first (Day 1) and last administration of investigational medicinal product (IMP), and will be outpatients for the rest of the trial. Subjects who receive aripiprazole IM depot 400 mg will stay in the unit for 21 days after administration of the first (Day 1), seventh (Day 169), and eighth (Day 197) doses of IMP. Subjects who are not able to accommodate the scheduled stays in the unit may be permitted to have some visits as outpatients with approval of the medical monitor. For any outpatient visit, an unscheduled C-SSRS will be performed.

Subjects enrolled to the sparse sampling schedule will be outpatients for all administrations of IMP but, at the discretion of the investigator, may be housed in the unit for up to 21 days after the first administration of IMP ([Section 3.1](#)). Subjects staying in the clinical unit may check in to the clinical unit on Day -1; however, all predose assessments will be performed on Day 1 prior to the administration of IMP.

While housed in the clinical unit, standard meals consisting of breakfast, lunch, dinner, and an evening snack will be provided at times that do not interfere with trial activities and assessments. There are no restrictions on food or water intake prior to administration of aripiprazole IM depot. Food and water will be permitted ad libitum according to the clinical unit's standard operating procedures.

Subjects will be required to present to the clinical trial site for efficacy and safety assessments and collection of PK samples on the days specified in [Table 3.7-1](#) for subjects enrolled to the sparse sampling schedule and in [Table 3.7-2](#) for subjects enrolled to the robust sampling schedule.

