### **3.7.2 Dietary Requirements**

With the exception of alcohol consumption, which is prohibited ([Section 4](#)), there are no other dietary restrictions in this trial.

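### SAP 8.5 applies fasting-based lipid and glucose classes to samples of unspecified fasting status, so the absolute treatment-emergent rates can include meal-related misclassification

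*SAP*

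**What the plan says.** SAP 8.5 plans incidences of treatment-emergent relevant changes in lipid parameters and glucose by formulation and disease type, and adds "though those blood samples are not required to be collected at the fasted state". The note under Table 8.5-1 states: "Classifications of lipids (refer to fasting lipid measurements) are used for lipid parameters and the American Diabetes Association Criteria are used for glucose". One baseline glucose class in that table is "Impaired Fasting Glucose 100~<126". Each row compares a baseline value with any post-baseline value. Some rows count a change from any baseline, including a glucose rise of at least 10 mg/dL and a triglyceride rise of at least 50 mg/dL.

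SAP Appendix 2 gives glucose two limits, at least 115 mg/dL fasting and at least 200 mg/dL non-fasting. All of its lipid limits are for fasting samples, beginning with "Total cholesterol, fasting", and there is no non-fasting alternative.

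Protocol 3.7.2 says that, alcohol aside, "there are no other dietary restrictions in this trial". Protocol 3.7.1 says "There are no restrictions on food or water intake prior to administration of aripiprazole IM depot"; that sentence is about dosing, not laboratory draws. Under the Protocol's schedules, chemistry is taken at screening, Day 1, Day 29 and Day 225 or early termination. SAP 5.1 takes the last evaluable value before injection as baseline.

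**The concern.** A fasting class has its intended meaning only for a fasted sample. Here a sample may be fasted or fed, and nothing in the published text lets the analyst tell which. Two consequences follow.

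First, the Appendix 2 rules need an input that the documents do not say will exist. Without it, a programmer cannot choose between the two glucose limits, or decide whether any lipid limit applies.

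Second, a subject who is fasted at baseline and fed later can cross a Table 8.5-1 threshold with no drug effect. Comparing one baseline value with any later value gives more than one chance to do so.

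Safety is the first primary objective, and Protocol 1.4 lists hyperglycemia/diabetes and dyslipidemia among the adverse reactions associated with this drug or its class. The published rates could be read as metabolic abnormalities when part of them reflects meals or ordinary variation.

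**Working it through.** The documents state no expected rate or variability for these analyses, so there is no planned figure to reproduce. The passages can be compared directly, and the size can be shown only under stated assumptions.

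**One value under three rules.** Take a glucose of 105 mg/dL at baseline and 130 mg/dL later. Table 8.5-1 counts a shift to High (130 ≥ 126) and a rise of 25 (≥ 10). Appendix 2 flags it if fasted (130 ≥ 115) and does not if fed (130 < 200). The result depends on a fact that may not be in the database.

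**Chance of a flag with no true change.** Inputs from the documents are one baseline value and two scheduled post-baseline draws (Day 29, Day 225). The within-subject SD σ is an assumption. Each difference from baseline is N(0, 2σ²). The two differences share the baseline value, so their correlation is 0.5. With threshold T, P(one draw) = 1 − Φ(T/(σ√2)) and P(either draw) = 1 − Φ₂(T/(σ√2), T/(σ√2); 0.5). These were evaluated by simulation with 400,000 draws.

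Glucose rise of at least 10 mg/dL, either draw:
- σ = 5: T/(σ√2) = 10/7.07 = 1.41; 13%
- σ = 10: 10/14.14 = 0.71; 37%
- σ = 15: 10/21.21 = 0.47; 47%
- σ = 20: 10/28.28 = 0.35; 52%

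Triglyceride rise of at least 50 mg/dL, either draw: 7% at σ = 20, 30% at σ = 40, 48% at σ = 80.

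Glucose shift from below 100 to at least 126 mg/dL, among subjects with baseline below 100 (assumed subject mean 95, between-subject SD 8): about 0% at σ = 5, 0.5% at 10, 4% at 15, 12% at 20. The class shift is much less exposed than the any-baseline row.

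**Adding an explicit meal effect.** Assume σ = 5 and a constant post-meal rise of 20 mg/dL, with each sample independently fed with probability q. The chance of a rise of at least 10 at either draw is 25.7% at q = 0.1, 39.2% at 0.3, 40.5% at 0.5, 20.5% at 0.9 and 13.3% at 1.0. All-fed equals all-fasted because a constant rise cancels. Mixed status, rather than non-fasting as such, drives the excess in this model.

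**Comparison between arms.** Suppose a share π of subjects in each arm is flagged by noise alone. The observed rate is π + (1 − π)p, where p is the true rate. Take assumed true rates of 20% and 10%, 129 per arm (planned enrolment, ignoring dropout) and a two-sided 5% test:
- π = 0: 20% versus 10%, difference 10 points, power 62%
- π = 0.25: 0.25 + 0.75 × 0.20 = 40.0% versus 0.25 + 0.75 × 0.10 = 32.5%, difference 7.5 points, power 24%

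If the true rates are equal, the observed difference stays at 0.

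**The case against.** The strongest reply is that this is one descriptive table whose limitation the SAP itself discloses. Other metabolic outputs are planned: change from baseline by visit (SAP 8.5), the non-fasting glucose limit (Appendix 2), weight change of at least 7% (Appendix 1), and weight-, glucose- and lipid-related events of special interest (SAP 8.10). The laboratory instructions and the eCRF are not in the published documents, so failure to capture fasting status cannot be established. All of this stands and limits the point. Disclosure does not, however, tell the analyst which limit applies or stop fed values entering fasting classes.

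A reader might infer more than the documents support:
- That the trial takes non-fasting blood. The SAP says only that fasting is not required; status is unspecified and may be mixed.
- That the rates largely count meals. No document figure supports this, the high percentages rest on assumed SDs, and the class shift is near 0% at SDs of 5 to 10.
- That 126 in Table 8.5-1 contradicts 200 in Appendix 2. One counts shifts from a baseline class and the other flags absolute values, so different cut-offs are not in themselves a conflict.

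A mandatory fast would also be hard to arrange at early-termination and unscheduled draws, with 34% dropout assumed. The SAP's COVID-19 provisions suggest that conduct was already under way, and a new fasting instruction cannot repair samples already drawn.

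**Conclusion.** The mismatch is in the text and holds. Absolute Table 8.5-1 rates should not be read as fasting abnormalities. Their possible inflation varies by row: 13% to 52% flagged with no true change on the glucose rise of at least 10 mg/dL, against about 0% to 12% on the shift from below 100 to at least 126. Both ranges assume within-subject SDs of 5 to 20 mg/dL and two post-baseline draws.

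Noise shared by the arms dilutes a real difference without biasing a null comparison. Equal noise is likely under randomization but not assured. On Day 29 the 400 mg arm has a dosing visit with a predose PK draw, while the 960 mg arm has a non-dosing visit with its PK draw between 8 AM and 2 PM. If laboratory samples are taken with the PK draws, time since a meal could differ by arm.

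It may be tempting to conclude that the metabolic part of the primary safety objective cannot be answered. The documents do not support that: the objective is general, it carries no metabolic hypothesis or margin, and the other outputs remain. This is a cheap and worthwhile correction to a descriptive safety table.

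**What to change.** - Record fasting status, or time since last meal, at every laboratory draw, including screening (which can become baseline), unscheduled and early-termination draws. Do not make fasting mandatory.
- Present Table 8.5-1 change criteria as fasting results only where both the baseline and the post-baseline sample are fasted. Apply the Appendix 2 fasting limits only to fasted samples.
- Classify other glucose values by the SAP's own non-fasting limit of at least 200 mg/dL.
- Where status was not recorded, label the rates as fasting status unknown, do not present them as fasting classes, and report lipid changes descriptively.

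The cost is one data field and some SAP wording. The downside is that fewer subjects contribute to the fasting table, possibly many fewer if few samples happen to be fasted. For samples already drawn without a record, only the labelling and descriptive reporting are available, and these need no change to trial conduct.
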